### **5.11.1 Active Follow Up (+/- 7 days)**

Participants will be followed monthly for 6 months following the last dose of treatment on study.

1. History, physical examination, height and weight
2. ECOG Performance Status
3. AE Assessment
4. Medications
5. CBC with differential, platelet count
6. Liver Functions and blood chemistries: Na, K, Cl, CO2, Ca, Mg, PO4, Creatinine, total bilirubin, direct bilirubin, alkaline phosphatase, AST, ALT, LDH
7. Beta-2 Microglobulin, CRP
8. TSH, Free T4, Free T3
9. Evaluation of creatinine clearance
10. Laboratory Disease Evaluation:
  - Quantitative serum immunoglobulin levels.
  - Serum protein electrophoresis (SPEP).
  - 24-hour urine collection to determine creatinine clearance and protein excretion, urine electrophoresis (UPEP) required for participants with +UPEP at baseline. Otherwise, random UPEP is permitted. If the random UPEP is positive, a 24-hour urine collection is required.
  - Immunofixation of urine and serum protein regardless of SPEP and UPEP results.
11. Vital Signs (including ambulatory O2 sat) per Section 11
12. Bone marrow and aspirate as per Section 11
13. Skeletal bone survey to include cranium, axial skeleton and proximal long bones or alternative imaging to capture areas of bone disease at months 1 and 6
14. Study tubes as per Section 10

### **5.11.2 Progression Free Survival (+/- 14 days)**

Participants will be followed every 3 months for 5 years. Participants will be followed until time of disease progression, at which time they will be followed for survival as outlined 5.11.4. At the time of disease progression

patients will have disease assessments and study bloods/aspirate as outlined in section 10.

1. Laboratory Disease Evaluation:

- Quantitative serum immunoglobulin levels.
- Serum protein electrophoresis (SPEP).
- 24-hour urine collection to determine creatinine clearance and protein excretion, urine electrophoresis (UPEP) required for participants with +UPEP at baseline. Otherwise, random UPEP is permitted. If the random UPEP is positive, a 24-hour urine collection is required.
- Immunofixation of urine and serum protein regardless of SPEP and UPEP results.

#### **5.11.3 Toxicity Assessment Visit (+/- 7 days)**

Participants taken off treatment due to disease progression or to start alternative anti-myeloma therapy at MD discretion will be required to do a toxicity assessment visit 30 days after the last dose of study treatment.

1. History, physical examination, height and weight
2. ECOG Performance Status
3. AE Assessment If patients have ongoing related AEs at the toxicity assessment visit, this should continue to be followed at least monthly, or as clinically indicated, until resolution.)
4. Medications
5. CBC with differential, platelet count
6. Liver Functions and blood chemistries: Na, K, Cl, CO2, Ca, Mg, PO4, Creatinine, total bilirubin, direct bilirubin, alkaline phosphatase, AST, ALT, LDH
7. TSH, Free T4, Free T3
8. Evaluation of creatinine clearance
9. Vital Signs (including ambulatory O2 sat) per Section 11

#### **5.11.4 Survival Follow-Up**

Participants will be followed in clinic or by phone every 6 months for 5 years from the last dose of treatment.

### **5.12 Agent Administration**

#### **5.12.1 Nivolumab**

Patients will be treated with Nivolumab 240 mg on days 1 and 15 of a 28-day cycle. Nivolumab will be given every two weeks ( $\pm 3$  days). Patients may be dosed no less than 12 days from the previous dose of drug.

Nivolumab is to be administered as a 60-minute IV infusion (+/- 10 minutes), using a volumetric pump with a 0.2/1.2 micron in-line filter at the protocol-specified dose. The drug can be diluted with 0.9% normal saline for delivery but the total drug concentration of the solution cannot be below 1.0 mg/mL. It is not to be administered as an IV push or bolus injection.

Vital signs (BP, HR, Temp, RR, O2 sat) will be taken within 15 minutes prior to start of nivolumab infusion and within 15 minutes following completion of the infusion.

#### **5.12.2 DC/MM Fusion Vaccine**

Patients will receive the DC/myeloma fusion vaccine/GM-CSF (vaccine) on day 1 of cycles 1, 2, and 3. Vaccine will be administered by subcutaneous injection with 100 ug GM-CSF given subcutaneously at the vaccine site on day of vaccination and daily for a total of 4 days of each cycle. The vaccine will be administered at least 1 hour following

Nivolumab infusion. On the first day of GM-CSF administration, 100 ug of GM-CSF subcutaneously will be administered subcutaneously. The patient will be trained to inject the remaining three GM-CSF injections (100ug dose once a day at the vaccination site) for self-administration subcutaneously at home.

### **5.13 General Concomitant Medication and Supportive Care Guidelines**

Patients started on systemic anti-neoplastic chemotherapy or immune suppression while on treatment will be taken off the study drug. The administration of live vaccinations while on treatment is prohibited. Short courses of corticosteroids for adverse events may be permitted after discussion with the Study Chair, [name].

### **5.14 Criteria for Taking a Participant Off Treatment**

Duration of therapy will depend on individual response, evidence of disease progression and tolerance. In the absence of treatment delays due to adverse event(s), treatment may continue for up to 6 cycles of nivolumab or until one of the following criteria applies:

- Disease progression by IMWG criteria, after the administration of study treatment
- Intercurrent illness that prevents further administration of treatment
- Unacceptable adverse event(s)
- Participant demonstrates an inability or unwillingness to comply with the oral medication regimen and/or documentation requirements
- Participant decides to withdraw from the protocol therapy
- General or specific changes in the participant's condition render the participant unacceptable for further treatment in the judgment of the treating investigator

Participants will be removed from the protocol therapy when any of these criteria apply. The reason for removal from protocol therapy, and the date the participant was removed, must be documented in the case report form (CRF). Alternative care options will be discussed with the participant.

When a participant is removed from protocol therapy and/or is off of the study, the relevant Off-Treatment/Off-Study information will be updated in OnCore.

### **5.15 Criteria for Taking a Participant Off Study**

Participants will be removed from study when any of the following criteria apply:

- Lost to follow-up
- Withdrawal of consent for data submission
- Death
- Disease progression by IMWG criteria, prior to the administration of study treatment

The reason for taking a participant off study, and the date the participant was removed, must be documented in the case report form (CRF). In addition, the study team will ensure Off Treatment/Off Study information is updated in OnCore in accordance with DF/HCC policy REGIST-101.

## **6. DOSING DELAYS/DOSE MODIFICATIONS**

Dose delays and modifications will be made as indicated in the following sections. The descriptions and grading scales found in the revised NCI Common Terminology Criteria for Adverse Events (CTCAE) version 4.0 will be utilized for dose delays and dose modifications. A copy of the CTCAE version 4.0 can be downloaded from the

CTEP website  
[http://ctep.cancer.gov/protocolDevelopment/electronic\\_applications/ctc.htm](http://ctep.cancer.gov/protocolDevelopment/electronic_applications/ctc.htm).

## 6.1 Dose Delays

To initiate cycle 1 of therapy with vaccine and nivolumab, participants must meet the eligibility criteria outlined in section 3.3.

Patients experiencing any of the following toxicities judged to be possibly or definitely related to study treatment will not receive further therapy.

- Grade 3 or higher non-hematologic toxicities that do not resolve within 14 days of onset;
  - Please note the following exceptions indicated in Appendix B that necessitate immediate discontinuation of therapy:
    - Grade 4 creatinine elevation
    - Grade 3 or higher pulmonary toxicity
    - ALT/AST or total bilirubin grade 3 or higher elevation
    - Grade 3 or higher adrenal insufficiency
    - Grade 3 or higher neurological adverse event
    - Grade 3 or higher myocarditis
- Grade 4 or higher non-hematologic toxicities;
- Grade 4 or higher hematologic toxicities that do not resolved within 7 days of onset;
  - Please note that this excludes lymphopenia, as mentioned in section 5.9.3;
- Grade 4 or higher nivolumab infusion reactions.
- Laboratory abnormalities that are not thought to be clinically significant (i.e. lymphopenia) will not be included in criteria for holding of therapy

Patients experiencing grade 3 non-hematologic toxicity, grade 2 immune associated toxicity as outlined in Appendix B, and grade 4 hematologic toxicity will have therapy held.

Patients not meeting these criteria may have therapy held for clinical reasons with the approval of the study PI or designee.

Patients who experience grade 4 hematologic toxicity that resolves to grade 1 or baseline within 7 days OR grade 3 non-hematologic toxicity that resolves to grade 0-1 within 14 days OR grade 2 immune associated toxicity requiring hold of therapy as outlined in Appendix B that resolves to grade 0-1 within 14 days may have therapy restarted UNLESS otherwise specified in Appendix B.

Therapy is restarted at the point of dose interruption so that all intended doses of vaccine and nivolumab are administered.

Patients experiencing recurrence grade 3 non-hematologic toxicity, grade 2 immune associated toxicity as outlined in Appendix B, and grade 4 hematologic toxicity will have therapy discontinued UNLESS otherwise specified in Appendix B.

To initiate cycles 2-6 of therapy, subjects must not have any evidence of TLT as outlined above or in section 7. In the event that the toxicity is clearly related to nivolumab alone (such as infusion reactions) and meets criteria for discontinuation, patients may continue to receive vaccine alone per protocol. Patients experiencing immune-related adverse events may be treated with corticosteroids (up to prednisone of 1 mg/kg or equivalent). Patients who improve to grade 1 or less in this context as outlined above AND who can be tapered to prednisone of 10 mg or equivalent or less may continue on therapy. There will be no dose modifications.

Treatment may be held for up to 14 days for unrelated adverse events, or as clinically indicated, at the discretion of the treating physician.

## 6.2 Management of Nivolumab-Related Infusion Reactions

Infusion reactions to Nivolumab may consist of fever, chills, rigors, headache, rash, urticaria, angioedema, pruritus, arthralgias, hypo- or hypertension, bronchospasm, or other symptoms. Infusion reactions should be graded according to NCI CTCAE version 4.0 guidelines.

**For Grade 1 symptoms:** (Mild reaction; infusion interruption not indicated; intervention not indicated) Infusion rate may be slowed or interrupted and restarted at 50% of the original infusion rate when symptoms resolve; if no further complications ensue after 30 minutes, the rate may be increased to 100% of the original infusion rate. Monitor patient closely.

The following prophylactic pre-medications are recommended for future infusions: diphenhydramine 50 mg (or equivalent) and/or paracetamol 325 to 1000 mg (acetaminophen) at least 30 minutes before additional nivolumab administrations, slowing infusion rate as above.

**For Grade 2 symptoms:** (Moderate reaction requires therapy or infusion interruption but responds promptly to symptomatic treatment [e.g., antihistamines, non-steroidal anti- inflammatory drugs, narcotics, corticosteroids, bronchodilators, IV fluids]; close observation for recurrence and treatment medications may need to be continued for 24-48 hours), and no further nivolumab will be administered at that visit.

Stop the nivolumab infusion, begin an IV infusion of normal saline, and treat the subject with diphenhydramine 50 mg IV (or equivalent) and/or paracetamol 325 to 1000 mg (acetaminophen); remain at bedside and monitor patient until resolution of symptoms. Corticosteroid or bronchodilator therapy may also be administered as appropriate. If the infusion is interrupted, then restart the infusion at 50% of the original infusion rate when symptoms resolve; if no further complications ensue after 30 minutes, the rate may be increased to 100% of the original infusion rate. Monitor patient closely. If symptoms recur, re administer diphenhydramine 50 mg IV, and remain at bedside and monitor the patient until resolution of symptoms.

The following prophylactic premedications are recommended for future infusions: diphenhydramine 50 mg (or equivalent) and (acetaminophen) (or paracetamol) 325 to 1000 mg should be administered at least 30 minutes before additional nivolumab administrations. If necessary, corticosteroids (recommended dose: up to 25 mg of IV hydrocortisone or equivalent) may be used.

**For Grade 3 or Grade 4 symptoms:** (Severe reaction):

**Grade 3 symptoms:** prolonged [*i.e.*, not rapidly responsive to symptomatic medication and/or brief interruption of infusion]; recurrence of symptoms following initial improvement; hospitalization indicated for other clinical sequelae [e.g., renal impairment, pulmonary infiltrates]).

**Grade 4 symptoms:** (life threatening; pressor or ventilatory support indicated). Nivolumab will be permanently discontinued:

- Immediately discontinue infusion of nivolumab. Begin an IV infusion of normal saline, and bronchodilators, epinephrine 0.2 to 1 mg of a 1: 1,000 solution for subcutaneous administration or 0.1 to 0.25 mg of a 1: 10,000 solution injected slowly for IV administration, and/or diphenhydramine 50 mg IV with methylprednisolone 100 mg IV (or equivalent), as needed. Patient should be monitored until the investigator is comfortable that the symptoms will not recur.
- In the event of anaphylaxis, follow institutional guidelines.
- In the case of late-occurring hypersensitivity symptoms (e.g., appearance of a localized or generalized pruritus within 1 week after treatment), symptomatic treatment may be given (e.g., oral antihistamine, or corticosteroids). Additional treatment prior to next dose as per guidelines above.
- Please note that late occurring events including isolated fever and fatigue may represent the presentation of systemic inflammation. Please evaluate accordingly.

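### Section 6.2 gives two incompatible instructions for a grade 2 nivolumab infusion reaction: no more drug at that visit, and a restart at half rate once symptoms resolve

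*Combined protocol and SAP*

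**What the plan says.** Protocol Section 6.2 sets the handling of infusion reactions by grade. The grade 2 text opens with a parenthesis describing a moderate reaction. After the parenthesis closes comes an unconditional clause: "no further nivolumab will be administered at that visit".

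The paragraph that follows gives the bedside steps for the same grade. It begins "Stop the nivolumab infusion, begin an IV infusion of normal saline", lists the drugs to give, and continues: "If the infusion is interrupted, then restart the infusion at 50% of the original infusion rate when symptoms resolve". It then allows a return to full rate if 30 minutes pass without further complications, and adds: "If symptoms recur, re administer diphenhydramine 50 mg IV, and remain at bedside". A separate paragraph deals with premedication before later infusions.

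Three other places bear on the point:

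- Section 5.12.1 sets 240 mg over 60 minutes (with a 10-minute tolerance), on days 1 and 15 of a 28-day cycle, and says "Patients may be dosed no less than 12 days from the previous dose of drug".
- Section 6.1 says that patients with "grade 3 non-hematologic toxicity, grade 2 immune associated toxicity as outlined in Appendix B, and grade 4 hematologic toxicity will have therapy held". It also says "Therapy is restarted at the point of dose interruption so that all intended doses of vaccine and nivolumab are administered", and lets therapy be held for clinical reasons in other patients if the study PI or a designee approves.
- The grade 3 description in Section 6.2 includes "recurrence of symptoms following initial improvement".

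**The concern.** The two grade 2 instructions apply to the same patient at the same moment and point in opposite directions. One ends nivolumab for the day; the other resumes it. Section 6.2 lists bronchospasm, angioedema and hypotension among the possible symptoms, so whether a patient who has just reacted is re-exposed within the hour or at a later visit is a real safety decision. As written, it depends on which sentence the treating staff act on.

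There is also a dosing consequence. If the infusion is not resumed, part of the 240 mg is not given at that visit, and the plan does not say whether a part-dose is made up. If the part-infusion counts as the previous dose (an assumption), the 12-day minimum in Section 5.12.1 governs when nivolumab can next be given. On day 1 of cycles 1 to 3 the choice also affects vaccine timing, since Section 5.12.2 requires the vaccine to follow the nivolumab infusion by at least 1 hour.

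**Working it through.** The plan states no figure on this point, so the main check is textual.

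**Can the two instructions be reconciled?**

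1. *Could the restart mean a later visit?* No. It is triggered when symptoms resolve, it sits among bedside monitoring steps, and it has a 30-minute rate step. Later infusions have their own paragraph.
2. *Does the conditional opening of "If the infusion is interrupted, then restart the infusion at 50% of the original infusion rate when symptoms resolve" mark off a separate case?* No. The same paragraph opens with "Stop the nivolumab infusion, begin an IV infusion of normal saline", so every grade 2 infusion is interrupted. If a grade 2 reaction were treated without interruption, continuing that infusion would still breach "no further nivolumab will be administered at that visit".
3. *Does Section 6.1 settle it?* No. "Therapy is restarted at the point of dose interruption so that all intended doses of vaccine and nivolumab are administered" follows the rules for therapy held for toxicity and does not say whether a stopped infusion resumes the same day. Sections 6.1 and 7 name infusion reactions only from grade 4.
4. *Do Sections 5.12.1 or 9.1.8 settle it?* No. They give infusion duration, and Section 5.12.1 adds the dosing interval.
5. *Does Appendix B settle it?* Its figures cannot be read here. Section 6.3 sends nivolumab events other than infusion reactions there, and the readable headings cover organ-specific events. The readable text does not address infusion reactions.
6. *Is the choice left to clinical judgement?* Both grade 2 instructions are directive. The grade 1 text is permissive about slowing or interrupting the infusion, so discretion was written in where it was wanted.

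**How much drug turns on the choice?**

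Inputs: 240 mg over 60 minutes (Section 5.12.1). The times at which the infusion is stopped are assumed, because the documents give none; a constant rate before the stop is also assumed.

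- Full rate: 240 / 60 = 4 mg/min. Half rate: 4 × 0.5 = 2 mg/min.
- Undelivered dose = 240 − 4 × (minutes infused).
- Restart with return to full rate: the first 30 minutes give 30 × 2 = 60 mg, and the rest runs at 4 mg/min.
- Restart at half rate throughout: undelivered dose / 2.

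| Stopped at (assumed) | Undelivered | Further infusion time, return to full rate after 30 min | Further infusion time, half rate throughout |
|---|---|---|---|
| 15 min | 240 − 60 = 180 mg | 30 + 120/4 = 60 min | 180/2 = 90 min |
| 30 min | 240 − 120 = 120 mg | 30 + 60/4 = 45 min | 120/2 = 60 min |
| 45 min | 240 − 180 = 60 mg | 30 + 0/4 = 30 min | 60/2 = 30 min |

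The return to full rate is optional in Section 6.2, so both columns are possible. Neither includes the wait for symptoms to resolve.

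**The case against.** The strongest reply is that withholding has its own support. Section 6.1 allows therapy to be held for clinical reasons with approval of the study PI or designee, so a physician who does not resume the infusion can be within the protocol. This stands, and it limits the point. A reader might infer that whatever staff do is a protocol breach; the documents do not support that. The firm conflict runs one way: a same-visit restart breaches an unconditional prohibition. The hold route needs an approval, though, and does not say what staff should do by default.

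A second reply is that this is a drafting slip. The prohibition hangs after a closed parenthesis and would fit naturally after "If symptoms recur, re administer diphenhydramine 50 mg IV, and remain at bedside". That is plausible, and it is why a wording correction is enough. Staff cannot be expected to infer it.

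A reader might also infer that recurrence after a restart has no rule. That goes too far. Recurrence meets the grade 3 description, "recurrence of symptoms following initial improvement", and Section 6.1 holds therapy for grade 3 non-hematologic toxicity. What is unclear is whether the permanent discontinuation stated after the grade 4 description in Section 6.2 also covers grade 3. That matters here only because one of the two possible corrections depends on it.

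**Conclusion.** The contradiction is real and confidence in it is high: the grade 2 text of Section 6.2 both forbids and directs nivolumab at the visit of the reaction, and no readable text says which governs. It should be corrected.

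Its size is a same-day re-exposure decision plus 60 to 180 mg of a 240 mg dose per affected infusion, for assumed stops at 45 to 15 minutes. A completed restart would add 30 to 60 minutes if the rate returns to full, or 30 to 90 minutes if it stays at half.

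A reader might want a count of affected patients. Section 8.1.1.1 lists infusion reactions of all grades together and gives no grade 2 share, so the documents do not support one. Nor is there any effect on sample size, power, the TLT definition or the 10-patient suspension rule.

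**What to change.** Keep one grade 2 rule in Section 6.2. The choice is the sponsor's.

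- **No same-day restart.** Delete the restart and rate-increase sentences from the grade 2 paragraph and keep the prohibition on further nivolumab at that visit. This is the simpler change.
- **One restart allowed.** Permit a single restart at half rate after the first grade 2 reaction resolves, and move the prohibition to the sentence on recurring symptoms. State there that recurrence meets the grade 3 description, and name the consequence intended: permanent discontinuation if the discontinuation line in Section 6.2 is meant to cover grade 3, otherwise a hold under Section 6.1.

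The cost is a wording amendment to Section 6.2 and a notice to sites. Sample size, visit schedule, TLT definition and the 10-patient rule stay as they are.

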## 6.3 Management of Other Nivolumab-Related AEs

Please refer to Appendix B: Dose Modifications for Nivolumab-related AEs.

#### **6.4 Management of DC/MM Vaccine Site Reaction**

If a patient experiences a grade 2 or higher (graded according to CTCAE v4.0) injection site reaction during the days when GM-SCF is administered, subsequent doses of GM-CSF may be held until the injection site reaction improves to grade 1 or less at the discretion of the treating investigator. On the day of subsequent vaccine administrations, patients will receive pre-medication with diphenhydramine (Benadryl) 25-50 mg and/or acetaminophen (Tylenol) 650-1000 mg to minimize potential allergic-related symptoms.

### **7. IDENTIFICATION OF TREATMENT LIMITING TOXICITIES**

Treatment limiting toxicities (TLT) will be defined as toxicity judged to be possibly or definitely related to the study treatment and meeting the following criteria:

- Grade 3 or higher non-hematologic toxicities that do not resolve within 14 days of onset;
  - Please note the following exceptions that necessitate immediate discontinuation of therapy:
    - Grade 4 creatinine elevation
    - Grade 3 or higher pulmonary toxicity
    - Grade 3 or higher ALT, AST or total bilirubin elevation
    - Grade 3 or higher adrenal insufficiency
    - Grade 3 or higher neurological adverse event
    - Grade 3 or higher myocarditis
- Grade 4 or higher clinically significant non-hematologic toxicities;
- Grade 4 or higher hematologic toxicities that do not resolve to grade 1 or baseline within 7 days of onset;
  - Please note that this excludes lymphopenia, as mentioned in section 5.9.3;
- Grade 4 or higher nivolumab infusion reactions.

Patients experiencing TLT will not receive further therapy

If 3 or more patients experience a TLT within the first 28 days of initiating therapy among the first 10 patients enrolled, then accrual will be suspended. TLTs will be defined per the above criteria with grades determined by CTCAE version 4.0 that are possibly, probably or definitely related to the study treatment. Patients will be monitored for the occurrence of TLTs during the first 28 days of treatment.

Once the 10th participant is enrolled, accrual will be paused until the 10th participant completes a full cycle of treatment (28 days) without experiencing any TLTs.

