## Myocarditis Adverse Event Management Algorithm

Patients on IV steroids may be switched to an equivalent dose of oral corticosteroids (eg, prednisone) at start of tapering or earlier, once sustained clinical improvement is observed. Lower bioavailability of oral corticosteroids should be taken into account when switching to the equivalent dose of oral corticosteroids.

Prophylactic antibiotics should be considered in the setting of ongoing immunosuppression.

ATG = anti-thymocyte globulin; BNP = B-type natriuretic peptide; ECG = electrocardiogram; IV = intravenous; MRI = magnetic resonance imaging

Adverse Reaction	Severity	Dose Delays
Other – excluding hematologic toxicities	Other Grade 3 adverse reaction: First occurrence	Withhold dose and resume when AE returns to Grade 0 or 1
	Recurrence of same grade 3 adverse reaction 	Permanently discontinue
	Life-threatening or Grade 4 adverse reaction	Permanently discontinue
	Requirement for 10 mg per day or greater prednisone or equivalent for more than 12 weeks	Permanently discontinue
	Persistent Grade 2 or 3 adverse reactions lasting 12 weeks or longer	Permanently discontinue

1. Laboratory abnormalities determined to be not clinically significant are not subject to this criteria, hematologic in nature or otherwise.

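### A related grade 3 event that resolves after day 14 must stop therapy under Sections 6.1 and 7, but the Appendix B 'Other' row says to resume

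*Combined protocol and SAP*

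**What the plan says.** **The stop.** Section 6.1 lists toxicities, possibly or definitely related to study treatment, after which no further therapy is given. One is "Grade 3 or higher non-hematologic toxicities that do not resolve within 14 days of onset". Section 7 uses the same criterion to define a TLT and adds "Patients experiencing TLT will not receive further therapy".

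**The restart.** Section 6.1 covers "grade 3 non-hematologic toxicity that resolves to grade 0-1 within 14 days" and says such patients "may have therapy restarted UNLESS otherwise specified in Appendix B". It continues: "Therapy is restarted at the point of dose interruption so that all intended doses of vaccine and nivolumab are administered". A similar deferral to Appendix B is attached to the rule on recurrent toxicity.

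**The cycle gate and the vaccine allowance.** The last part of Section 6.1 makes absence of any TLT a condition for starting each of cycles 2 to 6. It also lets vaccine continue alone when a toxicity that meets the discontinuation criteria is clearly due to nivolumab alone.

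**The appendix.** Section 6.3 says "Please refer to Appendix B: Dose Modifications for Nivolumab-related AEs". In the table that closes Appendix B, under the residual category that excludes hematologic toxicities, the entry for "Other Grade 3 adverse reaction: First occurrence" is "Withhold dose and resume when AE returns to Grade 0 or 1". A separate row in the same block discontinues permanently for grade 2 or 3 reactions that last 12 weeks or more.

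**The concern.** The body stops on two conditions, grade and time. The appendix row gives only the grade needed to resume. An investigator who goes from Section 6.3 to the table and follows the row would re-treat a patient whose event took longer than 14 days to settle. Section 7 calls that same event treatment-limiting and forbids re-treatment.

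The row covers real events. Section 8.1.1.1 lists fatigue as very common and myalgia and arthralgias as common with nivolumab. None has an organ algorithm among the Appendix B headings (GI, renal, pulmonary, hepatic, endocrine, skin, neurological, myocarditis), so each would fall to the 'Other' rows.

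At stake is whether two investigators would treat the same patient differently, one of them giving nivolumab after a TLT. The analysis is not affected.

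**Working it through.** **1. The plan's own TLT figure.** The only stated figure that depends on the TLT definition is the continuation table in Section 14.1. With n = 10, P(continue) = P(X ≤ 2) = Σ C(10,k) p^k (1−p)^(10−k) for k = 0, 1, 2. For p = 0.10, 0.20, 0.25, 0.30 and 0.40 this gives 0.9298, 0.6778, 0.5256, 0.3828 and 0.1673. The plan prints 0.930, 0.678, 0.526, 0.383 and 0.167. All five agree. The event is a TLT whichever re-treatment rule is followed, so the table does not change.

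**2. The rules side by side.** Take a related grade 3 arthralgia that starts the day after the first dose of cycle 1. Resolution is read as return to grade 0-1, the standard used in the Section 6.1 restart rule.

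| Course of the event | Sections 6.1 and 7 | Appendix B 'Other' rows |
|---|---|---|
| Grade 1 by day 14 from onset | Restart allowed | Resume |
| Grade 1 on day 18 from onset | TLT, no further therapy | Resume |
| Still grade 2 or 3 at 12 weeks | Already stopped at day 14 | Permanently discontinue |

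Only the middle line conflicts. The window runs from day 14 to 12 × 7 = 84 days, so it is up to 84 − 14 = 70 days wide.

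**3. Whether Section 6.1 settles precedence.** It refers to Appendix B in three places:
- a list of exceptions to the 14-day criterion, every one stricter (immediate discontinuation);
- restart after resolution within 14 days, unless Appendix B says otherwise;
- discontinuation on recurrence, unless Appendix B says otherwise.

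None is attached to the stop for an event unresolved at 14 days. The Section 7 sentence carries no exception. No sentence ranks the row against the 14-day stop for this case.

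**4. What the row alone could release.** Nivolumab is due on days 1 and 15 of each cycle; vaccine is due on day 1 of cycles 1, 2 and 3.
- Event starts after the day-1 dose and before the day-15 dose: the held day-15 nivolumab dose could be released. That is 1 nivolumab and 0 vaccine.
- Event starts after the day-15 dose: the next dose falls on day 1 of the next cycle, behind the no-TLT gate. That is 0 and 0.

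Any later-cycle nivolumab or vaccine would also require a breach of that gate. The documents give no rate for residual-category grade 3 events that resolve after day 14, so no expected number of patients is given.

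**The case against.** The strongest reply is that the texts can be read together: the row gives the grade at which treatment may resume, and the body adds the clock. Section 6.1 defers to Appendix B in named places and not here. Its listed Appendix B exceptions to the 14-day rule are all stricter. The 14-day stop, the TLT sentence in Section 7 and the cycle gate all point the same way.

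Much of this stands. A reader might infer that the plan gives no guidance on which rule applies; the documents do not support that, because the body's direction is plain even without a precedence sentence. What does not stand is that the appendix needs no correction. It carries its own clock, at 12 weeks and for grade 3 as well as grade 2. If the 14-day stop always applies, the grade 3 part of that row has little left to do for related events. The table therefore looks like a self-contained scheme, and an investigator could follow it in good faith.

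A second reply is that most Appendix B algorithms are figures not reproduced in the text. That is right, and the point is confined to the legible table rows.

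**Conclusion.** The point holds as a local inconsistency in a patient-level stopping rule. For a related, residual-category grade 3 event that resolves after day 14 and before week 12, the appendix row permits what Section 7 forbids. From the row alone, the size is at most one held day-15 nivolumab dose for an affected patient.

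Three stronger readings are tempting and are not supported:
- A reader might infer that every remaining dose is at risk: after the first dose of cycle 1, 11 of 12 nivolumab and 2 of 3 vaccine. The Section 6.1 gate blocks each later cycle, so that count needs further, separate breaches.
- A reader might infer that the appendix sets no time limit at all. That is true of the row but not of the block, which stops at 12 weeks.
- A reader might infer that the body always ends vaccine too. Section 6.1 lets vaccine continue alone when the toxicity is clearly due to nivolumab alone.

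The conclusion assumes that the event is attributed to study treatment and that resolution means grade 0-1. TLT status, the 3-in-10 accrual rule, n = 25 and the cut-off of 17 are unaffected.

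**What to change.** Amend the first-occurrence grade 3 row of the Appendix B 'Other' block to read, in substance: *withhold; resume only if the event returns to grade 0-1 within 14 days of onset; otherwise permanently discontinue nivolumab (Sections 6.1 and 7)*.

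Add one sentence stating that, for related grade 3 non-hematologic events, the 14-day limit takes precedence over the 12-week row. Without it, the 12-week row would keep suggesting a longer allowance. Leave the Section 6.1 vaccine-alone allowance as it is.

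The cost is one row and one sentence. The downside is that a few patients with slow-resolving events come off treatment, which Sections 6.1 and 7 already require. Sample size, decision rule and TLT table stay as they are.
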